9.3.3 Secondary endpoint variable(s) and analyses

- Differences in hepatic fat fraction [%], measured by MRI-PDFF after 6 months of intervention, between DHA and placebo will be estimated with the same model as the primary endpoint. The estimated difference will be displayed with its 95% confidence interval.
- Differences in hepatic fat fraction [%], measured by MRI-PDFF after 6 months of intervention, between Vitamin E and placebo will be estimated with the same model as the primary endpoint. The estimated difference will be displayed with its 95% confidence interval.
- Between group differences in anthropometric measures, after 3 and 6 months of DHA EE and/or Vitamin E intervention will be analysed with the same approach as the primary endpoint, using the relevant anthropometric measure at baseline as the respective baseline covariate and gender as a categorical covariate.
- Between group differences in inflammatory markers after 6 months of intervention and liver enzymes after 3 and 6 months of DHA EE and/or Vitamin E intervention will be analysed with the same approach as above and diabetes status as a categorical covariate included in the model.
- Between group differences in the FIB-4 score after 6 months of DHA EE and/or Vitamin E intervention will be analysed with the same approach as above.
- \circ Between group differences in plasma DHA and plasma α -tocopheryl after 3 and 6 months of intervention will be analysed with the same approach as above.
- Between group differences in SF-36 quality of life score after 6 months of DHA EE and/or Vitamin E intervention will be analyzed by ANCOVA with baseline score included in the model.
- Between group differences in dietary intake of LC-PUFA (i.e. DHA and EPA) will be assessed by the FFQ and analysed over time by repeated measures ANOVA with baseline level and site included in the model.

With blinded data, the residuals of the models will be analysed visually (QQ-plots, residual plots) to determine if the model assumptions (normality, variance homogeneity) are met. If necessary, variance-stabilizing transformations or non-parametric methods will be considered.

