15 APPENDICES

15.1 Appendix 1

DHA Food Frequency Questionnaire®

Subject ID #:	Initials:			Date:		
	F	M	L	M	M DD	YY

Estimate your consumption over the past 2 months of the following foods. Use the food model forms to help estimate portion sizes.

				Servings	DHA	EPA
1.	How many 3oz servir bluefish blue fin tuna cisco, smoked	ngs of the follor herring mackerel pollock	wing fish do you eat monthly ? sardines salmon whitefish		x 22	x 14
2.	How many 3oz servir bass calamari catfish drumfish flounder grouper halibut	ngs of the follor mussels perch redfish rockfish shark snapper sole	wing fish do you eat monthly ? squid swordfish trout tuna, canned (6oz can) whiting		x 10	x 5
3.	How many 3oz servir monthly? carp clams cod crab crayfish fish patties/squares	ngs of the follow fish sticks haddock lobster mullet oysters pike	wing fish/shellfish do you eat pompano scallops shrimp (14 med.) sturgeon		x 5	x 6
4.	How many 3oz servir eat monthly ?	ngs of liver (chi	cken, turkey or beef) do you		x 7	x 2
5.	How many egg yolks in cooking)?	do you eat we	ekly (including eggs yolks used		x 3	x 0.25
6.	How many 3oz servir including livers) do y		turkey or other poultry (not ?		x 5	x 3
7.	Any omega-3 dietary fish oil, Neuromins, I amount or strength	DHA Gold, high			mg/ d	mg/ d
			Su	ıb-Total:	DHA (mg/d)	EPA (mg/d)
			TOTAL= Rounded to Nearest	Whole #:		
					DHA (mg/d)	EPA (mg/d)
@ M-	rtak Biosciancos Corn	oration now D	SM Nutritional Products			

 $\ensuremath{\mathbb C}$ Martek Biosciences Corporation, now DSM Nutritional Products

15.2 Appendix 2

SF-36(tm) Health Survey

Instructions for completing the questionnaire: Please answer every question. Some questions may look like others, but					
each one is different. Please take the time to read and answer each question carefully by filling in the bubble that best					
represents your response.					
Patient Name:					
SID#: Date:					
Person heling to complete this form: back					
1. In general, would you say your health is:					
••Excellent					
□□Very good					
□□Good					
••Fair					
Poor					
Compared to one year ago, how would you rate your health in general now?					
••Much better now than a year ago					
Somewhat better now than a year ago					
□□About the same as one year ago					
□•Somewhat worse now than one year ago					
•••Much worse now than one year ago					
3. The following items are about activities you might do during a typical day. Does your health now limit you in these					

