# 8.0 Statistical Methods

Unadjusted descriptive statistics will be provided per measured time point. Continuous variables will be summarized with mean, standard deviation, median, and range. Categorical variables will be summarized with counts and percentages. All tests of significance are two-sided and considered significant at the 0.05 level. All confidence intervals presented will be 95% and two-sided. SAS version 9.4 or higher will be used for statistical analyses unless otherwise stated.

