The differences between intervention groups (DHA EE + vitamin E vs. PBO, vitamin E vs. PBO, DHA EE vs. PBO) in dietary intake of LC-PUFA, specifically DHA and EPA, will be assessed over time with a linear mixed model following an ANOVA approach. Fixed effects will include the intervention group, categorical time point (baseline, 1 month, 3 months, 6 months), and intervention group by time point interaction. A random intercept and a random time effect for subject nested within site will be included. For the random time effect, the covariance structure (e.g compound symmetry, unstructured) will be selected such that the AICC (corrected Akaike information criterion) is reduced. If a significant interaction effect is indicated, an interaction plot will be produced and the relevant pairwise comparisons between intervention groups and PBO at each time point (i.e. DHA EE + vitamin E vs. PBO, vitamin E vs. PBO, DHA EE vs. PBO) will be estimated along with a 95% confidence interval (CI) at each modeled time point. The Benjamini-Hochberg (false discovery rate) adjustment will be used for the 12 planned comparisons. Additionally, the model derived change from baseline to each follow-up time point will be estimated along with a 95% confidence interval.

For each model, the residuals of the model will be analyzed visually (QQ-plots, residual plots) to verify model assumptions (normality, constant variance, and homogeneity) are met. If necessary, a variance stabilizing transformation may be considered. The impact of the random effect(s) will be evaluated with the likelihood ratio test and may be removed if not significantly adding to the model.

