| r-ANOVA⁺ | Time-treatment
interaction p-value       |     |                       |        |           |
|          | Baseline estimate (95
% CI)              |     |                       |        |           |
|          | Baseline difference ++           |     |                       |        |           |
|          | 95% CI                                      |     |                       |        |           |
|          | p-value*                                    |     |                       |        |           |
|          | adjusted p-value**                          |     |                       |        |           |
|          | 1-month estimate
(95 % Cl)               |     |                       |        |           |
|          | 1-month change
from baseline (95%
CI) |     |                       |        |           |
|          | 1-month difference ++            |     |                       |        |           |
|          | 95% CI                                      |     |                       |        |           |
|          | p-value*                                    |     |                       |        |           |
|          | adjusted p-value**                          |     |                       |        |           |
|          | 3-month estimate
(95 % CI)               |     |                       |        |           |
|          | 3-month change
from baseline (95%
CI) |     |                       |        |           |

| 3-month difference**                        |  |
|---|--|
| 95% CI                                      |  |
| p-value*                                    |  |
| adjusted p-value**                          |  |
| 6-month estimate
(95 % CI)               |  |
| 6-month change
from baseline (95%
Cl) |  |
| 6-month difference ++            |  |
| 95% CI                                      |  |
| p-value*                                    |  |
| adjusted p-value**                          |  |

+ Mixed model for repeated measures ANCOVA

++ Model derived estimated difference from the PBO

\* p-value for the pairwise comparisons to the PBO

\*\* FDR correction for multiple comparisons between arms at multiple time points

|         |                         |                   | РВО | DHA EE +
vitamin E | DHA EE | vitamin E |

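### Dietary DHA and EPA intake: three of the 12 planned comparisons test arms at baseline, and the follow-up contrasts are not adjusted for baseline intake

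*SAP*

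**What the plan says.** SAP 8.3 analyses dietary DHA and EPA with a linear mixed model. Its fixed effects are intervention group, "categorical time point (baseline, 1 month, 3 months, 6 months), and intervention group by time point interaction". Baseline is therefore a response. There is no baseline covariate, and the arms are not constrained to share a baseline mean.

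Pairwise contrasts are conditional: "If a significant interaction effect is indicated, an interaction plot will be produced", and the three contrasts ("DHA EE + vitamin E vs. PBO, vitamin E vs. PBO, DHA EE vs. PBO) will be estimated along with a 95% confidence interval") are then made at each time point. On multiplicity the SAP says "The Benjamini-Hochberg (false discovery rate) adjustment will be used for the 12 planned comparisons". The next sentence adds model-based changes from baseline, with confidence intervals.

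The table shell for this endpoint in SAP 12.1 has a "Baseline difference" row, followed by a confidence interval, a p-value and an adjusted p-value.

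Protocol 9.3.3 describes the same endpoint as "analysed over time by repeated measures ANOVA with baseline level and site included in the model". SAP 8.1 takes baseline intake from the randomisation visit (Visit 2). The questionnaire in Protocol Appendix 1 opens with "Estimate your consumption over the past 2 months of the following foods", and it is also used at the 1-month call.

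**The concern.** Intake reported at the randomisation visit cannot show a treatment effect. A difference between randomised arms there is chance, yet three such tests share the false-discovery family with the nine that matter. Each follow-up contrast ignores what is known about a participant's earlier diet, so it carries avoidable variance, and any chance imbalance at baseline carries into it.

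The endpoint matters because Protocol 1.3.2 reports that compliance problems and contamination of the placebo group limited an earlier omega-3 trial, and Protocol 5.6 restricts omega-3 products and fatty fish. If the dietary comparison has low power, a null result says little about whether background intake stayed balanced.

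A smaller point concerns the 1-month wave: its recall period reaches back before treatment began.

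**Working it through.** **Count.** Three active arms against placebo at four time points: 3 × 4 = 12, the SAP's figure. Post-baseline only: 3 × 3 = 9. For the endpoints that SAP 8.3 models at 3 and 6 months, baseline is a covariate and the Holm family is 3 × 2 = 6. The same section therefore handles baseline in two different ways and gives no reason for treating diet differently.

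**Inputs from the documents.** Significance level: "All tests of significance are two-sided and considered significant at the 0.05 level" (SAP 8.0). Completers: 60/60/30/30 for combination, placebo, DHA EE and vitamin E (Protocol 9.3.7, SAP 7.0).

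**Inputs assumed.** Neither document gives an SD, a correlation or a target difference for intake. I work in SD units with equal correlation ρ between all visits (compound symmetry), complete data, and one single-agent arm shifted at months 1, 3 and 6.

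**Threshold.** The smallest Benjamini-Hochberg threshold is 0.05/12 = 0.0042 for 12 tests and 0.05/9 = 0.0056 for 9.

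**Variance.** With complete data the SAP's contrast at a visit is the difference in arm means at that visit. Its variance is σ²(1/n₁ + 1/n₀). Adjusting for baseline multiplies this by 1 − ρ².

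- ρ = 0.3: 0.91 remains, a fall of 9%.
- ρ = 0.4: 0.84 remains, a fall of 16%.
- ρ = 0.5: 0.75 remains, a fall of 25%.
- ρ = 0.7: 0.51 remains, a fall of 49%.

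For 30 against 60, the unadjusted standard error is √(1/30 + 1/60) = 0.224 SD, so a 0.5 SD shift is 0.5/0.224 = 2.24 standard errors. After adjustment it is 2.24/√(1 − ρ²) = 2.34, 2.58 and 3.13 for ρ = 0.3, 0.5 and 0.7. At the smallest threshold in each family, normal-approximation power is 27% unadjusted (12 tests) against 33%, 42% and 64% adjusted (9 tests).

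**Simulation of the full Benjamini-Hochberg step.** The table gives power for the shifted single-agent arm at 6 months, for a shift of 0.5 SD. The gate is a multivariate test of changes from baseline across arms, standing in for the SAP's interaction test. The same gate is applied to both analyses in the last two columns.

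| ρ | No gate: SAP, 12 unadjusted | No gate: 9 adjusted | Gate: SAP, 12 unadjusted | Gate: 9 adjusted |
|---|---|---|---|---|
| 0.3 | 31–34% | 40% | 15% | 21% |
| 0.5 | 31–34% | 52% | 21% | 34% |
| 0.7 | 31–34% | 73% | 27% | 63% |

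The unadjusted, ungated figure does not depend materially on ρ. For a 0.7 SD shift at ρ = 0.5, ungated power rises from 67% to 87%.

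**Which part matters.** Dropping the three baseline tests, with no adjustment, adds only about 4 points. The rest of the gain comes from baseline adjustment.

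**Effect on the gate.** Suppose baseline becomes a covariate and the gate stays as a group-by-time interaction over months 1, 3 and 6. A constant shift produces no interaction there, so the gate opens about 5% of the time. At ρ = 0.5, detection at 6 months falls to about 3–5%, against 21% (0.5 SD) and 59% (0.7 SD) under the current SAP.

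**Recall window.** The call is at day 30 ± 3 and recall covers about 60 days, so about 60 − 30 = 30 days precede randomisation. By months 3 and 6 the window lies wholly after it.

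**The case against.** The strongest reply is that the SAP does use baseline. With baseline as a time level, the group-by-time interaction compares changes from baseline between arms, so it is itself a test of drift. Simulated at ρ = 0.5 it detects a 0.5 SD shift 52% of the time and a 0.7 SD shift 86% of the time, close to the adjusted pairwise analysis (52% and 87%). The shell also reports within-arm changes from baseline. This stands: a reader might infer that the SAP ignores baseline, and that is wrong. But the interaction test does not say which arm differs or by how much. The contrasts that do are unadjusted, and the within-arm changes are not planned as differences between arms.

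A reader might also infer that this endpoint is the only safeguard against contamination. The documents do not support that. SAP 8.3 compares plasma DHA at 3 and 6 months with baseline in the model. SAP 6.5 classes placebo and vitamin E participants whose DHA rises by more than 26 µg/mL as non-compliant.

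On the protocol, including baseline level in the model most naturally means a covariate, but Protocol 9.3.3 does not use that word, so the departure rests on the natural reading.

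On recall, it is tempting to say that a 1-month change is halved. That assumes respondents average literally over the window. The food items ask for usual weekly or monthly servings, so the documents do not establish the size of any dilution.

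**Conclusion.** The point holds as a minor one. The SAP spends three of its 12 comparisons on baseline differences and leaves the arm-versus-placebo contrasts for diet unadjusted, unlike Protocol 9.3.3 and unlike its own treatment of other repeated endpoints. The direction of the loss holds for any non-zero correlation between baseline and follow-up. Its size rests on assumed values. At 0.5 SD the gain in 6-month power runs from about 6 points (gated, ρ = 0.3) to about 40 points (ungated, ρ = 0.7).

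It would be an over-reading to blame the loss mainly on the baseline tests, or to see a threat to the primary result. This is a supportive secondary endpoint, and the liver-fat model in SAP 8.2 already adjusts for its own baseline.

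**What to change.** Adjust the between-arm contrasts for Visit 2 intake in one of two ways:

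- Keep baseline as a response but constrain the arms to a common baseline mean. The interaction gate then stays meaningful.
- Use baseline as a covariate with responses at months 1, 3 and 6. Replace the gate with a joint test of intervention group and group-by-time, or drop it.

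In either case, apply Benjamini-Hochberg to the nine post-baseline contrasts for each outcome, and delete the baseline p-value and adjusted p-value rows from the shell in SAP 12.1. Descriptive baseline summaries can stay.

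Treat the 1-month wave as descriptive, or interpret it with a note on the recall window. Leave the questionnaire as it is, since Protocol 7.3.6 describes it as validated.

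The cost is a few sentences in SAP 8.3 and an edited table shell. No new data or participants are needed.

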# 8.4 Exploratory Endpoint Analyses

The interaction between intervention groups and each of PNPLA3, HSD17b, and haptoglobin SNPs, as well as with the specified categorical demographic and baseline variables (section 4.3), on the 6-month hepatic fat fraction will be evaluated with the model specified in the primary endpoint analysis (section 8.2) where the interaction between intervention group and respective variable (i.e. SNP, categorical variable) will also be included. A separate model for each will be constructed for each exploratory interaction. Pairwise comparisons of DHA EE + vitamin E vs. PBO, vitamin E vs. PBO, and DHA EE vs. PBO will be estimated for each genotype / category along with 95% confidence intervals and presented in forest plots.

Transcriptomics (Tx) analysis of the PBMC gene expression will follow a discovery approach. The analyses will be performed internally at DSM. In brief, the gene expression workflow will be performed as defined by the Partek Software (https://www.partek.com/). The large data set will be first visually explored using different techniques like heat maps, clustering and principal component analysis (predefined by the Tx software application). This will also trigger the thresholds to be used in further processing. ANOVA pairwise group comparisons (placebo vs the different treatments) will be applied with the goal to identify genes that are significantly differently expressed. The contrast method of Fisher's least significant difference (LSD) will be used (Gene expression workflow, Partek Software) and q-Values (FDR) will be calculated to correct for multiple testing. The q-values will be set after inspection of the whole Tx data set, but will be between q = 0.05 - 0.15, if possible. The filtering will use the change fold of +1.2 fold up- and -1.2 fold down regulation versus the placebo group with the lowest p-values

2017-1088 (PUVENAFLD) SAP Version 4.0

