7.1.3 Blood sample assessment

Clinical chemistry: Glucose, HbA1c, ALT, AST, GGT, ALK-P, eGFR/creatinine clearance, creatinine, insulin, bilirubin, (**note:** for **ALT and AST** reference ranges for HH flags are to be used to determine clinical significance (CS))

Lipid panel: total cholesterol, HDL-cholesterol, LDL-cholesterol, oxidized LDL, TGs; **Hematology**: standard panel including complete blood count with automated differential including platelets, and coagulation panel INR, and Hep A (HAVIgM) test at screening, and **Inflammatory markers** (e.g. CK-18, TNF α , IL-6) will be analysed by a central lab.

Fatty acid analyses and analyses of LC-PUFA-derived oxylipins will be performed using plasma samples at the DSM Clinical Laboratory, [name]. Approximately 1.5 mL of plasma/subject/time point (V1, V3, V4) will be aliquoted and shipped frozen on dry ice in batches from the central lab to DSM.

500uL plasma for α -tocopheryl measurement (from V1, V3, V4) will be shipped frozen on dry ice in batches from the central lab to DSM Nutritional Products:

DNP R&D Analytics, NIC-RD/A Sample Registration Office, c/o Warenannahme, [name] Phone: [name] Fax: [name]

Transcriptome analysis of Gene Expression: in a subset of 40 subjects (~10 subjects/treatment arm), whole blood (~2ml) will be collected in PAXgene blood RNA tubes. Samples will be collected at Screening V1 and at Visit 4 and will be shipped frozen using dry ice along with other blood samples to the central lab the day it is drawn. Samples will be batched shipped frozen from the central lab to DSM Nutritional Products, Kaiseraugst, Switzerland for analysis.

Genotype analyses

An aliquot of whole blood (0.5ml) from each subject will be used for DNA extraction to identify those with single-nucleotide polymorphisms (SNP) i.e. PNPLA3, HSD17b and haptoglobin. Samples will be collected at Screening V1 and will be shipped frozen using dry ice along with other blood samples to the central lab the day it is drawn. Samples will be batched shipped frozen from the central lab to Indiana University for analysis.

An additional 1 ml plasma (aliquoted into [2] 0.5ml tubes) will also be collected at V1 and V4, shipped frozen on dry ice to central lab and stored for future NAFLD biomarker use.

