9.3.4 Exploratory variables

Transcriptome analysis of gene expression will be performed in peripheral blood mononuclear cells in a subset of (n=40) subjects (~10 subjects/ treatment arm). Changes in gene expression from baseline to end of treatment (6 months) will be examined. The analyses will be conducted by DSM. Briefly, differentially expressed genes will be analysed by ANOVA. The false discovery rate (q values) will be used to correct for multiple testing. Using the global gene expression profiling results, an extensive pathway analysis (e.g. MetaCore program and/or Ingenuity Pathway Analysis) will be conducted to better understand gene regulation, mechanisms of action and activated pathways by the various treatments in this NAFLD population.

Between group differences in plasma LC-PUFA-derived oxylipins will be analysed by ANCOVA using the relevant baseline oxylipin level as a covariate.

Sub-set analyses of PNPLA3, HSD17b and haptoglobin SNPs will be conducted on the Primary endpoint to assess potential genotypic responses to treatment.

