#### 4.3 Exploratory Endpoint(s)

- The difference after 6 months of intervention between specified treatment groups (vitamin E + DHA combination vs. placebo, vitamin E vs. placebo, DHA vs. placebo) on the hepatic fat fraction [%], adjusted for baseline, stratified by the following single nucleotide polymorphisms (SNPs):
  - PNPLA3 genotype (CC versus CG + GG)
  - HSD17b genotype (GA + GG versus AA)
  - Haptoglobin genotype (\*2/\*2 versus \*1/\*2 + \*1/\*1)
- The difference after 6 months of intervention between specified treatment groups (vitamin E + DHA combination vs. placebo, vitamin E vs. placebo, DHA vs. placebo) on the hepatic fat fraction [%], adjusted for baseline, stratified by the following demographic and baseline variables:
  - Type II diabetes (yes/no)
  - Sex (male/female)
  - Baseline FIB-4 score (low risk [<1.3] versus indeterminate/high risk [≥1.3])

  - BMI (<30 kg/m^2 [underweight/healthy] versus  $\geq$ 30 kg/m^2 [overweight/obese])
  - Age (cutoff defined by the median of the baseline distribution)
  - ALT level at baseline (cutoff defined by the median of the baseline distribution)
- Transcriptome analysis will be performed using the gene expression data of peripheral blood mononuclear cells in a subset of approximately 40 subjects that complete the intervention. Changes in gene expression from baseline to end of treatment will be examined.
- The difference after 6 months of intervention between specified treatment groups (vitamin E + DHA combination vs. placebo, vitamin E vs. placebo, DHA vs. placebo) on the LC-PUFA derived oxylipins

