#### Table 1: Schedule of assessments

2017-1088 (PUVENAFLD) SAP Version 4.0

| Compliance-Pill count      |   |   |   | Х | Х | Х |
|----------------------------|---|---|---|---|---|---|
| Adverse event
reporting |   |   | Х | Х | х | Х |
| ConMeds                    |   |   | х | х | Х | Х |
| FFQ                        | Х |   | х | х | Х | Х |
| SF-36 questionnaire        |   |   | х |   |   | Х |
| Biosample collection ¶     |   | Х |   |   |   | Х |

\* fasted blood draw required and ALT, AST, Alk-P, bilirubin is measured 2x

\*values obtained at screening (except vital signs and FFQ) will be considered 'baseline' values

#HAVIgM to be performed unless negative results in past 3 years

oxylipins measured only at V1 and V4.

Skinner Lifetime Drinking Questionnaire and AUDIT given at V0 Screening

 Reminder phone calls at months 2,4 and 5 are advised to assist with retention and check on subject compliance, no diet fluctuations, ConMeds, and AEs.

\*\* Additional time may be allowed between study visits with approval and subsequent protocol deviation.

^ Audit questionnaire - Self-report version is collected at V0, V3 and V4 and the interview is only conducted during the 1-month phone call

¶ Refer to lab manual for sample collection table - Exploratory analyses include gene expression at V1 and V4 in a subset of 40 subjects, and PNPLA3, HSD17b, haptoglobin genotyping at V1.

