# 6.4 Subgroups

Subgroup analyses will be performed for the exploratory endpoint pertaining to the transcriptomic analysis of the PBMC gene expression. In order to obtain 40 subjects (~10 subjects / treatment arm) in the PBMC gene expression analysis set, samples from the first 55 subjects enrolled and randomized will be obtained and analyzed.

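### The gene-expression analysis names neither its response nor V1 expression as a covariate; adjusting for V1 would be more precise at almost no cost

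*SAP*

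**What the plan says.** **Endpoint.** SAP 4.3 states: "Changes in gene expression from baseline to end of treatment will be examined". Protocol 9.3.4 has the same statement with the time point added: "Changes in gene expression from baseline to end of treatment (6 months) will be examined".

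**Sampling.** Protocol 7.1.3: "Samples will be collected at Screening V1 and at Visit 4". The footnote to the SAP schedule of assessments agrees: "Exploratory analyses include gene expression at V1 and V4 in a subset of 40 subjects". SAP 6.4 gives the target size: "In order to obtain 40 subjects (~10 subjects / treatment arm) in the PBMC gene expression analysis set".

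**Test.** Protocol 9.3.4 says that "differentially expressed genes will be analysed by ANOVA". SAP 8.4 adds that "ANOVA pairwise group comparisons (placebo vs the different treatments) will be applied with the goal to identify genes that are significantly differently expressed", with Fisher LSD contrasts, q-values and a filter at 1.2-fold up or down relative to placebo. Neither text names the response variable or a baseline term.

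**Neighbouring endpoints.** The primary endpoint (SAP 8.2), most secondary endpoints (SAP 8.3), the oxylipins (protocol 9.3.4, SAP 8.4) and the conditional ELF and Pro-C3 analysis (SAP 8.5) all use ANCOVA with the baseline value in the model. Oxylipins and gene expression share one protocol section, and only the oxylipins are given a baseline covariate.

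**The concern.** Two analyses would comply with SAP 8.4 as written. One compares V4 levels between arms. The other compares V4 minus V1 changes. They can produce different gene lists, and the plan does not choose between them.

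Whichever is meant, a measurement that is already being paid for is not used as well as it could be. A V4-only comparison leaves all stable differences between people in the error term. A change score removes them by subtraction but carries the full noise of the V1 sample into the response. Letting the data estimate how much of V1 to subtract, as ANCOVA does, avoids both losses. With about 10 subjects per arm, and with the resulting gene lists passed on to pathway programs, precision is the scarce resource in this analysis.

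**Working it through.** The documents give no power, effect size, SD or V1-V4 correlation for gene expression, so there is no figure of the plan's own to reproduce. The check compares the precision of the candidate analyses.

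**Inputs**
- Samples at V1 and V4 (protocol 7.1.3; SAP schedule footnote).
- About 10 subjects per arm in four arms (SAP 6.4).
- V1-V4 correlation r of a gene's expression: *assumed*, 0.3 to 0.8.
- Equal variance at V1 and V4: *assumed*.

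**Formulas**, as variance of an arm contrast relative to a V4-only analysis:
- V4-only ANOVA: 1
- Change-score ANOVA: 2(1 − r)
- ANCOVA on V1: 1 − r²

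So ANCOVA relative to V4-only is 1 − r². Relative to a change score it is (1 − r²) / [2(1 − r)] = (1 + r)/2. Example at r = 0.7: 1 − 0.49 = 0.51; 2 × 0.3 = 0.60; 0.51/0.60 = 0.85.

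| r | V4-only | Change score | ANCOVA | ANCOVA as % of V4-only | ANCOVA as % of change score |
|---|---|---|---|---|---|
| 0.3 | 1.00 | 1.40 | 0.91 | 91% | 65% |
| 0.5 | 1.00 | 1.00 | 0.75 | 75% | 75% |
| 0.7 | 1.00 | 0.60 | 0.51 | 51% | 85% |
| 0.8 | 1.00 | 0.40 | 0.36 | 36% | 90% |

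The two gains run in opposite directions: where V4-only loses most (high r), the change score loses least.

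**What this means at 10 per arm.** One gene, two-sided 0.05, before any FDR step; noncentral t with 36 error df, or 35 with the covariate.

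| r | Power for a 1-SD difference: V4-only / change / ANCOVA | Difference detectable with 80% power (SD): V4-only / change / ANCOVA |
|---|---|---|
| 0.3 | 59% / 45% / 62% | 1.29 / 1.52 / 1.23 |
| 0.5 | 59% / 59% / 71% | 1.29 / 1.29 / 1.12 |
| 0.7 | 59% / 80% / 86% | 1.29 / 1.00 / 0.92 |
| 0.8 | 59% / 93% / 95% | 1.29 / 0.81 / 0.77 |

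To match ANCOVA with 10 per arm, a change score needs 10/0.65 = 15.4, 10/0.75 = 13.3 and 10/0.85 = 11.8 per arm at r = 0.3, 0.5 and 0.7. V4-only needs 10/0.91 = 11.0, 10/0.75 = 13.3 and 10/0.51 = 19.6.

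**Simulation** (5,000 trials per setting). Power for a 1-SD difference, V4-only / change / ANCOVA: 59/46/61% at r = 0.3, 58/57/69% at 0.5 and 59/79/85% at 0.7. With no true difference, the rejection rate was 4.3% to 5.5% for all three analyses.

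**A group-by-visit model is not a further option.** With two visits and complete pairs, the subject-blocked group-by-visit contrast is (mean V4 − mean V1 on active) − (mean V4 − mean V1 on placebo). That is the change-score comparison, with the same variance.

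**Arm sizes.** SAP 6.4 reaches its 40 by sampling the first 55 randomized. Under 65/65/35/35 allocation these would split about 55 × 65/200 = 17.9 in each large arm and 55 × 35/200 = 9.6 in each small one. The power figures would shift with the arm sizes; the variance ratios do not depend on them.

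**The case against.** The strongest reply is that the plan is brief here, not wrong. SAP 8.4 describes itself as a summary and defers to a named software workflow. Its silence on model terms does not exclude them: for dietary intake, SAP 8.3 uses the ANOVA label for a model with time (baseline included), a group-by-time interaction and subject-level random effects. SAP 4.3 and protocol 9.3.4 both say that change is examined, and SAP 4.3 limits the subset to subjects who complete the intervention, which suits paired data. On that reading V1 is used, and what remains is a preference between two valid analyses in a discovery exercise.

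Most of this stands. A reader might infer from SAP 8.4 that the V1 sample goes unused. The documents do not support that: a change score uses V1 by subtraction and fits the stated endpoint better than a V4-only test. A reader might also infer that chance baseline differences between small arms would pass as treatment effects. Under randomization they add noise, not bias, and the simulated error rates stay near 5%. Nor can the V1 sample be said in general to be worth a doubling of the subset: that holds only against V4-only at an assumed r of 0.7 (19.6 against 10 per arm). Against a change score at the same r, the equivalent is 11.8 per arm.

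What the reply does not answer is that the response is still unnamed. SAP 8.4 specifies the contrast method, the q-value range and the fold threshold, all of which presuppose a response and a model. The fold filter is expressed against placebo, so a V4-only run would also comply. And ANCOVA is more precise than a change score across the whole assumed range.

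**Conclusion.** The point holds as a gap in specification and a modest, inexpensive loss of efficiency. Neither document names the response or a baseline covariate for gene expression, and either permissible reading is valid but less precise than adjusting V4 for V1.

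The size rests on an assumed correlation and on equal variances at the two visits. At r = 0.3 to 0.8, ANCOVA has 65% to 90% of the variance of a change score, the likelier reading, and 91% to 36% of that of V4-only. The gain nearly vanishes against a change score at very high r (variance ratio 0.95 at r = 0.9, from 1.9/2) and against V4-only at low r (0.96 at r = 0.2). Apart from one degree of freedom, ANCOVA does not do worse than either, so the choice does not require knowing r. The single-gene power figures are illustrative and precede the FDR step.

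Type I error is not at issue. The analysis is exploratory, and the primary, secondary and safety conclusions are unaffected.

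**What to change.** In SAP 8.4, state that for each gene the V4 log2 expression is modelled on treatment group, with that gene's V1 log2 expression as covariate. State also that the q-values and the 1.2-fold filter are taken from the baseline-adjusted contrast of each active arm with placebo. The rest of the workflow can stay as it is. A group-by-visit contrast should not be offered as an equivalent improvement, for the reason shown in the working.

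The cost is one error degree of freedom per gene. Subjects without both samples drop out, as they also would from a change-score analysis. Because the covariate differs from gene to gene, and the documents do not show that the standard Partek workflow accepts one, a short separate program may be needed. No additional samples or visits are required.
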